Data Analysis: As in our pilot study, we will define "likely cognitive impairment" as a score ≤ 2 on the MiniCog; while we are aware it is by no means a gold standard, it is based on a well validated cutoff that serves our purpose of identifying patients who may need special approaches during the perioperative period. All analyses will be repeated in the subset of individuals with the greatest degree of cognitive impairment based upon a MiniCog score of (0-1) in order to understand why these individuals were not identified as cognitively impaired. We will first test the sensitivity of standard procedures compared to systematic procedures with MiniCog defined impairment or severe impairment. We will also compare sensitivity and specificity of the standard vs. systematic approach, and vs. the published sensitivity of 75% in comparable populations. As a secondary outcome, we will try to understand the full relationship among our four assessments, for instance whether systematic chart review and patient/informant reports detect individuals not detected by standard MiniCog cutoffs, as such individuals would be important to include as part of a broad "impairment" outcome for Aim 2 and consider in

subsequent work for special care in the perioperative period. Similarly, if we see patients who have received a formal evaluation of cognitive status in a memory clinic, by a primary care physician, or neuropsychological testing, we will try to understand qualitatively how MiniCog scores compare to such evaluations. Another secondary outcome will be how well patient/informant report can augment chart review when the patient does not have a primary care physician within our network. Differences between sensitivities and specificities will be compared using standard methods using confidence intervals.

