We will use logistic regression with any delirium as the outcome and cognitive impairment as defined by the MiniCog cutoff (or level of cognitive function as defined by the ordinal MiniCog score, modeled as best fits the data) in univariate analyses and in multivariate models adjusting for demographics (age, gender, education), baseline functional and medical covariates (ASA functional status, METs, frailty). Analogous analyses for our secondary outcomes will use logistic, linear, or Cox proportional hazards models to assess the relationship of MiniCog scores to these outcomes. In univariate analyses, we will compare change in WHODAS in MiniCog-impaired vs. unimpaired patients using Wilcoxon U test and with ordinal MiniCog score using Spearman rank order correlation. Multivariate analyses will model change in WHODAS (ranked or transformed for best model fit) as a function of MiniCog impairment status (or ordinal value as above), controlling for age, gender, education, comorbidity index, and frailty. In exploratory analyses, patients with and without postoperative delirium will be analyzed separately and compared.

Assays performed using blood collected between from the current study will be analyzed in the grant Circulating Extracellular Vesicles as Biomarkers of Postoperative Delirium (grant submission number 1R21 AG061696-01). Co-investigator [name], is the PI of the above grant; no changes to the current protocol will be made for this analysis.

Risks and Discomforts:

Overall, this study poses low risks for the subjects. The sources of risk are of two types in this study, 1) participation in the interviews and cognitive test and 2) the risk of breach of confidential information. The first “risk” of the study is the time necessary to participate in the study assessments. However, in our pilot study, patients viewed the interactions with the research staff as very positive and enjoyable. It is possible that some of the assessments may pose the risk of fatigue or emotional distress. Should a patient become tired or distraught, the interview will be halted. A related “risk” of participation is the potential breach of confidentiality and privacy of the Protected Health

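### The delirium model does not say whether the MiniCog cutoff or the ordinal score carries the test of Objective 2; if the delirium data choose, a 5% test runs at about 7–13%

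*Combined protocol and SAP*

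**What the plan says.** Data Analysis first defines likely cognitive impairment "as a score ≤ 2 on the MiniCog". For Objective 2 it then states: "We will use logistic regression with any delirium as the outcome and cognitive impairment as defined by the MiniCog cutoff". A bracket directly after this offers an alternative exposure: "level of cognitive function as defined by the ordinal MiniCog score, modeled as best fits the data". Both univariate and adjusted models are planned.

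Delirium is not called primary, but the next sentence treats the other outcomes as secondary: "Analogous analyses for our secondary outcomes will use logistic, linear, or Cox proportional hazards models". I therefore take delirium as the main outcome for Objective 2.

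Two neighbouring statements bear on the point. Of patients whom chart review or informants identify but MiniCog misses, the section says "such individuals would be important to include as part of a broad" impairment definition for Aim 2, with no rule for whether or when this happens. The adjusted model for change in WHODAS allows the outcome to be "ranked or transformed for best model fit".

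No significance level, primary exposure form, fit criterion or multiplicity rule is given.

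**The concern.** In a logistic model of delirium, how well a coding of MiniCog fits can be judged only against the delirium data. If that judgement selects the coding, and the selected coding is then tested on the same patients as if it had been fixed beforehand, the p-value ignores the selection. Objective 2 asks whether preoperative impairment predicts postoperative outcome, and the Monitoring and Quality Assurance section says that publication is intended to document whether there is such a risk factor. A reader of that paper would take a p-value below 0.05 at face value. With several codings available and none named in advance, it would be weaker evidence than it looks.

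**Working it through.** The plan gives no alpha, power or sample-size derivation, so there is no figure of its own to reproduce. The check is how often a test rejects when MiniCog and delirium are unrelated.

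**Inputs from the documents**
- Cutoff: MiniCog 2 or less (Data Analysis).
- Pilot prevalence of impairment: 24% overall and 33% at age 75 or more. Four of 289 pilot patients scored 0, and 4/289 = 1.4% (background section).
- Older cohort: 500 or 750; Subject Selection gives both figures. Neither changes the finding.
- Delirium: 15–80% in older surgical patients (background section; not a design assumption).

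**Assumed**
- Two-sided 5% level.
- Delirium rate of 15–30%.
- Scores 0 to 5 in proportions 1.4, 6.6, 16, 22, 25 and 29%. The first three sum to 24%, as in the pilot; the rest of the shape is a guess. One setting used 33% at 2 or less.
- Univariate logistic likelihood-ratio tests, with the form of lowest AIC selected. The plan names no criterion.
- 3,000 to 4,000 runs per setting. The Monte Carlo standard error near 8% with 3,000 runs is √(0.08 × 0.92 / 3000) = 0.5 points.

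**Analytic bound.** If two tests at 5% were independent, the chance that at least one rejects would be 1 − 0.95² = 9.75%; for three, 1 − 0.95³ = 14.3%. The cutoff and the score come from the same measurement and are correlated, so two forms should fall between 5% and 9.75%. Each uses one degree of freedom, so the lower AIC and the smaller p-value pick the same form.

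**Simulated false-positive rates (ranges over settings and repeat simulations)**

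| How the exposure is set | Rate |
|---|---|
| One form fixed in advance (cutoff or linear) | 4.6–5.7% |
| Better-fitting of cutoff and linear score | 7.0–8.9% |
| Best-fitting ordinal form only (linear, quadratic, categorical) | 9.9–11.0% |
| Best-fitting of cutoff, linear, quadratic, categorical | 11.5–13.0% |

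**Broad definition.** Here an assumed random 10% or 20% of patients flagged by chart or informant were added to those at 2 or less. If this definition is fixed without sight of delirium and tested alone, the rate is 4.3–5.1%, so there is no inflation. If it is tested beside the cutoff and the better result is kept, the rate is 6.9–8.0%.

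**Cost of fixing a form.** With 500 patients, 20% delirium and an assumed linear trend, power was about 48% for the cutoff and 66% for the linear score. A steeper assumed slope gave 70% and 84%.

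**The case against.** The strongest reply is grammatical. The phrase about best fit attaches to the ordinal score, the cutoff is fixed, and nothing says that fit decides between the two. The univariate WHODAS plan runs both a two-group test and a rank correlation, which suggests that both forms may simply be reported. This is a fair reading, but it does not remove the problem. Letting fit choose among ordinal codings alone already gives about 10–11%. Reporting both forms with neither named as primary leaves the reader free to rely on the better one.

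It is also true that the study is observational and states no alpha, so the inflation is relative to a conventional level that I have assumed.

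Several stronger readings are tempting, and the documents do not support them:
- **That broadening impairment after Objective 1 by itself inflates error.** Objective 1 uses baseline information, not delirium. A broad definition settled on that basis keeps the nominal rate.
- **That broadening abandons the tool named in the hypothesis.** The Objectives section speaks of impairment and of screening and names no instrument.
- **That the WHODAS scale choice does the same harm.** Picking an outcome scale by residual fit gave 5.2–5.6% in a null simulation with 500 patients. Only picking the smallest p-value raised it (7.6–8.3%), and the plan does not propose that.
- **That the repeat in patients scoring 0–1 is another rival coding.** The plan presents it as a repeat, to understand why those patients were missed. It is not counted above.

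**Conclusion.** The point holds in a limited form. The plan leaves the exposure form of its main model open, and the wording on the ordinal score invites the delirium data to settle it. If they do, a nominal 5% test has a false-positive rate of about 7–9% with the two simplest forms and about 10–13% once quadratic and categorical codings are tried, against about 5% for one fixed form.

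These sizes rest on the assumed 5% level, score distribution, delirium rates and AIC selection, and on univariate models. The further choice between univariate and adjusted results is not counted. If the investigators fix the form before looking at delirium, there is no inflation, but the text does not commit them to that. A reader might also infer a biased odds ratio or intervals that are too narrow. Only rejection rates were computed, so no size is claimed for either.

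**What to change.** Add to Data Analysis, before any delirium data are analysed:

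1. One named primary exposure form for the delirium test of Objective 2, with its significance level. MiniCog 2 or less versus 3–5 is the natural choice because the section already defines that cutoff. A linear score fixed in advance is equally valid.
2. The other form as a named secondary analysis, reported whatever its fit. If both are to carry the claim, test each at 0.05/2 = 0.025.
3. Any broad chart or informant definition as a named secondary analysis, with its rule settled without sight of delirium outcomes.

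This costs a few sentences and no new data. The downside to weigh is power: if risk changes steadily across the score, the cutoff gives some away (about 48% against 66% in the setting above). The investigators should choose between the two forms with that in view.

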Our overriding hypothesis is that preoperative cognitive impairment is a risk factor for poor surgical outcomes in seniors and that preoperative screening is superior to standard or systematic clinical processes for identifying at-risk patients.

Objective 1. Assess the marginal benefit of structured preoperative cognitive screening relative to standard or systematic preoperative evaluation for identifying seniors with likely cognitive impairment.

Objective 2. Determine whether preoperative cognitive impairment predicts postoperative outcome.

Objective 3. Determine whether other preoperative variables (mood, social support, history of depression, pain, and health and functional status) predict postoperative outcome.

Subject Selection: This project is designed as a prospective, single-center observational study. The cohort will consist of 500 consenting subjects \geq 70 years of age who present to the BWH Weiner Center for Preoperative Evaluation (CPE) prior to elective thoracic surgery (specifically, thoracoscopic lung resection, lobectomy, thoracotomy, or esophagectomy) or to neurological anterior, posterior cervical, thoraco, or lumbar spine surgery performed by neurosurgeons or orthopedic spine surgeons. 250 subjects undergoing thoracic surgery will be recruited and 500 subjects undergoing spine surgery will be recruited. These ages are chosen as significant clinical data demonstrate increased cognitive impairment in community dwelling elders. Eligibility criteria include: patients \geq 70 years of age with an ASA physical status of I-III presenting for elective thoracic, or orthopedic anterior or posterior cervical, thoraco, or lumbar spine surgery. Exclusion criteria will include history of stroke (not including TIAs) or brain tumor, uncorrected vision or hearing impairment (unable to see pictures or read or hear instructions); limited use of the dominant hand (limited ability to draw); and/or inability to speak, read, or understand English.

An additional cohort of 50 patients aged 45-60 undergoing elective neurological posterior thoracolumbar spine surgery or orthopedic spine surgery with an ASA physical status of I-III will be recruited through the BWH Weiner Center for Preoperative Evaluation (CPE). Eligibility and exclusion criteria will be the same as the aged 70 and older cohort, barring age. The purpose of enrolling this small younger subject population is to compare biomarkers between the two groups.

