After obtaining consent, study staff will gain information about the patient's age and years of education. Study staff will administer standard instruments to assess mood (Geriatric Depression Scale-Short [GDS], a 15-item self-report questionnaire, and the Beck Anxiety Inventory [BAI]), The Amsterdam Preoperative Anxiety and Information Scale [APAIS], a brief, 6-item self-report questionnaire), social support (MOS Social Support Survey, a 12-item self-report questionnaire), pain (the Brief Pain Inventory Short-Form), frailty (the FRAIL scale assessing fatigue, resistance, ambulation, illness, and loss of weight), a risk assessment prior to surgery (MEDIA) measuring previous difficulties with memory, episodes of confusion, and cognitive enhancing medications, physical activity (the International Physical Activity Questionnaire – Short Form), and health and functional status (basic and instrumental activities of daily living [ADLs and IADLs, RAND 36-SF, and the WHODAS respectively]). The World Health Organization Disability Assessment Schedule 2.0 (WHODAS) is an alternative to the SF36 to measure physical health and disability. Past diagnosis of

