depression and pain noted on the patient's preoperative evaluation form will be recorded, as well as past history of delirium or other post-anesthetic complications, use of hearing and/or hearing aids, and medical comorbidites. In addition, patients will be asked if they've had a fall within the last 6 months, whether they've been evaluated for a change in memory or thinking, who accompanied them to their appointment, their employment status and their living situation (alone, institutionalized, living with family members) in a patient survey. The study staff will also administer the MiniCog, a simple cognitive screening tool that takes just 2-4 min to complete and has little or no education, language, or race bias. In addition, the Animal Fluency test will be administered, which is a short cognitive screen that takes one minute to complete. Patients will also complete the self-report cognitive assessment CANTAB Insight Cognitive Exam, using an iPad developed by Cambridge Cognition. This 10 minute assessment measures cognitive health on five axes: executive function, processing speed, attention, working memory, and episodic memory through three cognitive tests: Matching Patterns, Working Memory, and Pairs Associates Learning Tests. Other measures of cognitive impairment will be obtained by study staff through: documentation on the patient's standard preoperative form, patient or informant report of diagnosis or evaluation for cognitive impairment or memory concerns, and systematic medical record review. Each enrolled patient will receive a business card listing the investigators' contact information and be advised to expect a follow up telephone call 6 months and 1 year after surgery to verify data elements and reassess functional outcome.

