During their routine preoperative blood draw the phlebotomist will be provided with one 10mL heparinized blood tube, one 5mL heparinized blood tube and one 5mL non heparinized blood tube labeled with only the patient's study ID number that will be returned to the investigative team and processed within 30 minutes of the blood draw. If the phlebotomist is not able to obtain a sample during the patient's preoperative appointment, a sample will be drawn by a study staff member trained by one of the anesthesiologists, or a nursing or physician member of the anesthesiology team prior to incision instead. 200 μ L of this sample will be sent to a Partner's Core Facility for analysis of the APOE gene, specifically for the e4 allele which has been shown to be linked in the development of late-onset Alzheimer's and delirium. The presence of the E4 allele will be included in our multivariate analysis for the development of postoperative delirium. Genetic results will not be shared with participants, nor entered into the medical record. 20mL of blood will also be obtained on postoperative days 1-3 by a study staff member trained by one of the

anesthesiologists, or a nursing or physician member of the anesthesiology team. Total, the proposed collection is 80mL.

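### The delirium model omits the comorbidity index used in the WHODAS model, without a stated reason, so some residual confounding by comorbidity, of unknown size, may remain in the MiniCog odds ratio

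*Combined protocol and SAP*

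**What the plan says.** All the model statements are in the Data Analysis section of the combined protocol and SAP.

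- **Delirium (logistic regression).** MiniCog status is tested in "multivariate models adjusting for demographics (age, gender, education") and "baseline functional and medical covariates (ASA functional status, METs, frailty"). No comorbidity index is listed.
- **WHODAS change.** The multivariate model is fitted "controlling for age, gender, education, comorbidity index, and frailty". It has the index, but not ASA or METs.
- **Secondary outcomes.** "Analogous analyses for our secondary outcomes will use logistic, linear, or Cox proportional hazards models". No covariates are named.

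Three other places bear on the point.

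- Study Procedures adds a further delirium covariate: "The presence of the E4 allele will be included in our multivariate analysis for the development of postoperative delirium". The list in Data Analysis is therefore not complete.
- Study Procedures defines frailty as "frailty (the FRAIL scale assessing fatigue, resistance, ambulation, illness, and loss of weight"), so one of its five components is illness. It also has staff record "use of hearing and/or hearing aids, and medical comorbidites" at baseline, so the raw material for an index is collected.
- Subject Selection admits patients "with an ASA physical status of I-III presenting for elective thoracic" or spine surgery, so ASA has at most three levels.

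The comorbidity index is not named, defined or scored anywhere.

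**The concern.** MiniCog groups are not randomised. The background presents cognitive impairment as an independent cause of poor outcome, and Objective 2 asks whether it predicts postoperative outcome. A claim of independence is only as good as the adjustment set behind it.

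By putting an index in the WHODAS model, the authors treat comorbidity as a confounder. That model also contains frailty, so they did not regard frailty as a replacement for the index. It is hard to see why the reasoning should apply to disability but not to delirium, complications, readmission or death.

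If impaired patients have more disease than unimpaired patients with the same ASA grade, METs and frailty, and if disease raises the risk of the outcome, part of the comorbidity effect will be credited to MiniCog. That error runs towards the study hypothesis.

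**Working it through.** **Step 1. The covariate lists side by side.**

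| Covariate | Delirium | WHODAS change | Secondary outcomes |
|---|---|---|---|
| Age, gender, education | yes | yes | not stated |
| Frailty (FRAIL) | yes | yes | not stated |
| ASA | yes | no | not stated |
| METs | yes | no | not stated |
| APOE e4 | yes (Study Procedures) | no | not stated |
| Comorbidity index | no | yes | not stated |

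The sentence on secondary outcomes comes directly after the delirium model and calls these analyses analogous. The natural reading is that they take the delirium list, and so also lack the index. This is an inference.

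**Step 2. How large could the residual confounding be?** The documents give no sample-size calculation, significance level or comorbidity figure, so there is no planned figure to reproduce. What follows is an illustration on assumed inputs.

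Inputs from the documents: 24% impaired (pilot data in the background); delirium 15% and 30%, taken from the low end of the quoted 15-80%; n = 750 (Subject Selection gives both 500 and 750 for the older cohort).

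Assumed inputs: a true MiniCog odds ratio of 1.0; a comorbidity score C with SD 1 that raises the odds of impairment and of delirium by the same factor per SD (1.25, 1.5 or 2.0); a two-sided 5% test.

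Model, with M for impairment and D for delirium:

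- logit P(M) = a + ln(OR) × C
- logit P(D) = b + ln(OR) × C, with no M term
- the analysis regresses D on M and a proxy P = √R² × C + √(1 − R²) × noise

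P stands for ASA, METs and frailty together, and R² is the share of C's variance that they capture. Large-sample results from 1,000,000 simulated patients, where a range covers the two delirium rates:

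| Comorbidity OR per SD | R² = 0 | R² = 0.5 | R² = 0.75 | R² = 1 (index in the model) |
|---|---|---|---|---|
| 1.25 | 1.05 | 1.02 | 1.01 | 1.00 |
| 1.5 | 1.17 | 1.08-1.09 | 1.04 | 1.00 |
| 2.0 | 1.50-1.52 | 1.25 | 1.12 | 1.00 |

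Type I error uses a normal approximation at n = 750: Φ(b/SE − 1.96) + Φ(−b/SE − 1.96), where b is the spurious log odds ratio. At R² = 0.5 it is 0.05, 0.06-0.07 and 0.16-0.22 for the three strengths. At R² = 0.75 it is at most about 0.09.

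R² = 0 is shown only as a bound. It does not describe the plan, which does adjust for illness burden in part. R² = 1 assumes that the index measures comorbidity without error.

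**Step 3. What the extra term costs.** The Data Analysis list gives 7 terms: MiniCog plus six covariates, each as one term. At 15% delirium:

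- N = 750: 750 × 0.15 = 112.5 events; 112.5/7 = 16.1 per term, and 112.5/8 = 14.1 with the index.
- N = 500: 500 × 0.15 = 75 events; 75/7 = 10.7, and 75/8 = 9.4 with the index.

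Counting APOE e4 as well, the step is from 8 to 9 terms: 14.1 to 12.5 (N = 750) or 9.4 to 8.3 (N = 500).

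**The case against.** The strongest reply is that the delirium model already adjusts for illness burden. ASA grades systemic disease, METs measure functional capacity, and illness is one of the FRAIL components. This stands in part. A reader might infer from the missing index that comorbidity is not adjusted for at all in the delirium model; the documents do not support that. What remains is residual confounding. The reply is not complete, because ASA is limited to I-III, METs measure capacity and not disease, illness is one of five FRAIL components, and the authors themselves add an index on top of frailty for WHODAS.

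Second, every strength in the illustration is assumed. This stands. With odds ratios of 1.5 per SD and R² = 0.5, the spurious odds ratio of 1.08 to 1.09 is less than half a standard error at n = 750 (ln 1.09 = 0.086, against a standard error of about 0.2). Only the strongest setting inflates type I error much.

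Third, a reader might infer that the plan drops the index from the secondary-outcome models. It does not say so, because it names no covariates for them. If the natural reading is wrong, those models have no stated adjustment set, which also needs correcting.

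Fourth, outcome-specific adjustment sets are legitimate. Delirium on days 1-3 and WHODAS change at 6-12 months are different outcomes, so it would go too far to say that unequal sets make the two results impossible to interpret. The objection is to the lack of a reason for this particular difference.

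**Conclusion.** The point holds as an unexplained omission. Data Analysis uses a comorbidity index for WHODAS change and leaves it out for delirium, in an unrandomised comparison meant to show that impairment predicts outcome. ASA, METs and the FRAIL scale remove part of the confounding by comorbidity; what remains is of unknown and possibly negligible size.

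If the existing covariates capture half to three quarters of comorbidity, the spurious odds ratio in the illustration runs from 1.01 to 1.25. These figures rest on assumed associations of 1.25 to 2.0 per SD with both impairment and delirium. If comorbidity does not differ by MiniCog status at a given level of ASA, METs and frailty, the bias is near zero. The direction favours the hypothesis only if comorbidity is positively related to both impairment and outcome.

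The same concern extends to the secondary outcomes only by the natural reading of a sentence that lists no covariates. The change is worth making because it is cheap and the covariate is already planned.

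**What to change.** In Data Analysis:

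1. Add the comorbidity index to the delirium model, which then reads: MiniCog, age, gender, education, ASA, METs, frailty, APOE e4 and the index.
2. State the covariates for the complication, length-of-stay, readmission and mortality models, and include the index in them.
3. Define the index: which of the recorded comorbidities count and how they are scored. Leave out any dementia or cognitive item, so that the index does not adjust away the exposure.
4. For rare outcomes such as 30-day mortality, prespecify a reduced covariate set or a penalised model.

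One identical set for every outcome is optional. If the sets differ, give the reason.

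The cost is wording and a definition. No new data are needed, since comorbidities are already recorded at baseline. Each model gains one parameter that partly overlaps ASA and frailty. This is a small price for delirium, but a real one for rare outcomes, hence item 4.

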But does it matter? We contend the answer is 'yes'⁸ and conceptualize cognitive impairment as a form of brain failure that, like heart failure, arises from multiple causes but leads independently to poor outcomes. Evidence supports this reasoning. First, cognitive dysfunction is a risk factor for adverse life events.²² At a minimum, therefore, cognitive screening may help identify those least likely to benefit from the surgery. Second, routine clinical interactions, whether in primary care or hospital settings, are insensitive for detecting cognitive impairment or even frank dementia,^{13,17,23} an observation we confirmed in our pilot study (Preliminary Data). Failure to recognize the problem could lead to suboptimal outcomes in a surgical setting if patients cannot recall what is expected of them postoperatively in terms of activity restrictions, wound care, medication regimens, and rehabilitation. Third, many seniors experience subtle and long-lasting executive dysfunction postoperatively that is independent of the specific anesthetic or surgical procedure, suggesting the patient's preoperative cognitive function is a predisposing factor.²⁴⁻²⁶ Fourth, some evidence indicates poor cognitive status increases complication risk, undermines the chance of a good outcome, and adds to the cost of care. In hospital delirium is a prime example, as it occurs in 15-80% of older surgical patients and contributes to poor outcomes.²⁷⁻³⁰ Although pre-existing cognitive impairment is an established risk factor for delirium, we seldom know a patient's cognitive status preoperatively because it is not currently assessed. Pre-existing cognitive impairment may also be a risk factor for serious non-cognitive morbidity^{31,32} or mortality in geriatric patients having major elective operations¹⁹⁻²¹ but data on non-cognitive outcomes are limited and no such association has been tested in a naturalistic, real-world setting (i.e. screening by regular preoperative evaluation center staff) such as we propose. Nonetheless, it is noteworthy that brief screening tests like the MiniCog were sufficient to detect such relationships and that guidelines issued jointly by the American College of Surgeons (ACS) and the American Geriatrics Society (AGS) strongly recommend routine preoperative cognitive assessment and specifically mention the MiniCog, detailed history, and informant questionnaire³—precisely the tools we propose to use. Still, perhaps because the data justifying the recommendation are sparse, it has not been widely adopted.

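### The multivariable WHODAS analysis models change only; a baseline-adjusted model should be prespecified beside it as a supporting analysis, because the two answer different questions

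*Combined protocol and SAP*

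**What the plan says.** The Objectives section sets "Objective 2. Determine whether preoperative cognitive impairment predicts postoperative outcome". For function, Data Analysis first compares change in WHODAS between MiniCog groups with a Wilcoxon test, and relates it to the ordinal MiniCog score with a Spearman correlation. It then states: "Multivariate analyses will model change in WHODAS (ranked or transformed for best model fit) as a function of MiniCog impairment status" (or the ordinal score), "controlling for age, gender, education, comorbidity index, and frailty".

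Preoperative WHODAS is not in that covariate list. It is not in the delirium model's list either, which names "baseline functional and medical covariates (ASA functional status, METs, frailty". No other section adds a baseline-adjusted WHODAS model.

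The score itself is available. Study Procedures lists among the preoperative instruments "health and functional status (basic and instrumental activities of daily living [ADLs and IADLs, RAND 36-SF, and the WHODAS respectively", and repeats WHODAS 6 to 12 months after surgery. Frailty, the covariate closest to function, is measured separately: "frailty (the FRAIL scale assessing fatigue, resistance, ambulation, illness, and loss of weight".

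**The concern.** MiniCog status is observed, so patients who screen as impaired may already be more disabled before surgery. Frailty and comorbidity may absorb part of such a difference, but the FRAIL items are only a partial proxy for the WHODAS score.

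The planned model asks whether MiniCog groups change by different amounts. Objective 2 can also be read, for function, as asking whether MiniCog predicts follow-up WHODAS among patients with the same preoperative WHODAS. No planned model answers that. The background text says the authors "conceptualize cognitive impairment as a form of brain failure that, like heart failure, arises from multiple causes but leads independently to poor outcomes". This is an analogy and does not define a target of estimation, but it makes the second question a natural one for readers.

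At stake is interpretation. With the change model alone, a reader cannot tell how far a result, including a null one, reflects different starting points.

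**Working it through.** **Inputs from the documents.** The outcome and covariates are as quoted. Impairment is a MiniCog score of 2 or less. In the pilot, 24% of 289 patients were impaired. Subject Selection gives the older cohort as 500, but also says "250 subjects undergoing thoracic surgery will be recruited and 500 subjects undergoing spine surgery will be recruited", which sums to 750. I use N = 500 unless stated.

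**Inputs not in the documents.** WHODAS SDs, the baseline to follow-up correlation r, the baseline gap, alpha and power are all assumed. Triplets below are for r = 0.4/0.6/0.8. Baseline SD is 1, follow-up SD is s, tests are two-sided at 5%. The plan states no figure to reproduce.

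**Step 1: how the two estimates relate.** Let D be the MiniCog difference in baseline WHODAS after the listed covariates, and b the slope of follow-up on baseline in the adjusted model. In linear models with the same covariates, the unadjusted follow-up difference is (adjusted estimate) + bD, and the change estimate subtracts D from it. Hence (adjusted) - (change) = (1 - b)D. On ranked or transformed scales this is approximate.

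**Step 2: size of the difference.** Assume a raw gap of 0.25 SD, half absorbed by frailty, so D = 0.125. If frailty explains 15% of each score, b = s(r - 0.15)/0.85. For s = 1, 1 - b = 0.71/0.47/0.24; times 0.125 this is 0.09/0.06/0.03 SD.

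**Step 3: precision with no gap and no covariates.** Var(change) = 1 + s² - 2rs; Var(follow-up given baseline) = s²(1 - r²). For s = 1: 1.20/0.84 = 1.43, 0.80/0.64 = 1.25, 0.40/0.36 = 1.11.

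| s | Estimates differ by (SD) | Excess residual variance, change model |
|---|---|---|
| 1 | 0.09/0.06/0.03 | 43/25/11% |
| 1.25 | 0.08/0.04/0.01 | 19/6/0% |
| 0.8 | 0.10/0.07/0.05 | 86/66/56% |

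Without covariates b = rs, so s = 1.25 with r = 0.8 gives b = 1 and no loss. With the assumed frailty covariate and s = 1, the excess is 55/31/13%, so frailty does not remove it.

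The difference detectable with 80% power is 2.80 × √variance × k. At N = 500, k = √(1/120 + 1/380) = 0.1047. For s = 1, change versus adjusted: 0.32 v 0.27, 0.26 v 0.24, 0.19 v 0.18 SD. At N = 750 (k = 0.0855): 0.26 v 0.22, 0.21 v 0.19, 0.15 v 0.14 SD.

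**Step 4: how often the models disagree at the 5% level.** Simulation on ranks, N = 500, 24% impaired, complete follow-up, 0.25 SD gap half absorbed, 1,500 studies per setting. The chance floor is the disagreement with no gap and no effect (5,000 studies per setting).

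| s | Groups truly change equally | No MiniCog effect given baseline | Chance floor |
|---|---|---|---|
| 1 | 15/11/8% | 12/9/8% | 6/5/5% |
| 1.25 | 11/5/3% | 10/5/5% | 5/4/3% |
| 0.8 | 27/20/16% | 15/14/12% | 7/6/6% |

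A repeat check put the floor at about 3 to 8% overall. The excess over the floor when groups change equally is about 9/6/3 points (s = 1), 6/1/0 (s = 1.25) and 20/14/10 (s = 0.8). If frailty absorbs none of the gap, the s = 1 rates rise to 47/28/16% and 32/23/13%. That is a worst case, since the plan also adjusts for four other covariates.

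**Step 5: direction.** If impaired patients start worse and the groups truly change equally, the adjusted model shows a false decline, in favour of the study hypothesis. If MiniCog has no effect given baseline, the change model makes impaired patients appear to improve, against the hypothesis.

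**The case against.** The strongest reply is that nothing is wrong with the plan. Change in WHODAS is a clear target, used consistently in the univariate and multivariable analyses, and it answers one fair reading of Objective 2. In a non-randomised comparison the adjusted model is no safer. It can produce a false result in the direction the investigators expect, and if long-standing cognitive impairment caused the preoperative disability, it removes part of the association of interest. Leaving baseline out is therefore not an anti-conservative choice when impaired patients start worse. Apart from the 24% and the cohort size, every input above is assumed, and much of the disagreement between models is chance.

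All of that stands, and it limits the point to a supporting analysis. It does not show that the second question is answered anywhere in the plan, or that a reader could judge the role of starting disability from the change model alone.

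**Conclusion.** The point holds as a minor improvement to the functional-outcome part of Objective 2. The planned model is valid for the question it asks; a second reasonable question goes unanswered although the data for it will be in hand.

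Under the assumptions shown, the two estimates differ by 0.01 to 0.10 SD. The precision cost of the change model ranges from none (b close to 1) to 86% excess residual variance. Both figures depend on a gap, SD ratio and correlation that the documents do not give.

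A reader might infer that the change model is biased and should be replaced, or that omitting baseline WHODAS would often reverse the conclusion. The documents support neither. They give no baseline WHODAS by MiniCog status, neither model is automatically unbiased here, and the disagreement rates are mostly modest once the chance floor is subtracted (near zero at s = 1.25 and r = 0.8). The delirium analysis is not affected.

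**What to change.** Keep the planned change model. Add, as a prespecified supporting analysis, a model of follow-up WHODAS on baseline WHODAS, MiniCog and the same covariates.

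- Fix the scale in advance (for example, ranks of both scores) instead of choosing it by model fit.
- Use the same follow-up assessment in both models. Study Procedures mentions calls at 6 months and 1 year and also a 6 to 12 month WHODAS window.
- Report both estimates with intervals, and the baseline WHODAS difference between MiniCog groups.
- State the question each model answers: whether the groups change by different amounts, and whether MiniCog predicts follow-up function given preoperative function.
- State that statistical significance will not decide which model supports the conclusion.
- Note each model's possible error, including over-adjustment if cognition caused the preoperative disability.

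The cost is some SAP wording and one extra regression. No new data are needed and no patients are lost, because every change score already requires a baseline score. The remaining cost is that two results may differ and will need the stated interpretation.
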